11.3 Calculation or derivation of patient reported outcome variables – Not Applicable

11.4 Calculation or derivation of pharmacokinetic variables

The pharmacokinetic (PK) analyses will be performed at AstraZeneca R&D. The actual sampling times will be used in the PK calculations. If necessary, the PK properties of dapagliflozin will be evaluated by population PK methodology and reported in a separate PK report, including estimates of population mean PK parameters, between-patient variability as well as predictions of individual PK parameters (e.g. renal function on CL/F) may be identified and quantified. A detailed population PK analysis plan will be prepared prior to data base lock.

11.5 Calculation or derivation of pharmacodynamic variable(s) – Not Applicable

11.6 Calculation or derivation of pharmacogenetic variables – Not Applicable

11.7 Calculation or derivation of health economic variables – Not Applicable

12. STATISTICAL METHODS AND SAMPLE SIZE DETERMINATION BY ASTRAZENECA

A comprehensive Statistical Analysis Plan (SAP) will be prepared and finalised before the unblinding of the data.

The statistical analysis will be done by Statistics & Programming Department, AstraZeneca.

12.1 Description of analysis sets

The decision to include or exclude patients from each analysis set will be made at the clean file meeting, where the study team statistician and physician will attend, prior to the unblinding of the data.

12.1.1 Efficacy analysis set

The evaluation of efficacy will be performed for the full analysis set as well as for the per-protocol analysis set. The primary efficacy evaluation will be based on the full analysis set.

12.1.1.1 Full analysis set

The full analysis set will include all randomised patients who received at least one dose of study medication, and who have a non-missing baseline value and at least one post-baseline efficacy value for at least one efficacy variable. The patients will be analysed according to the treatment group to which they were randomised, regardless of the actually treatment taken.

12.1.1.2 Per protocol analysis set

The per-protocol analysis set – being a subset of the full analysis set – will include all patients of the full analysis set without major protocol deviations which may affect the study outcome significantly. Regardless of the number of patients not included in the per protocol analysis set, a set of pre-defined major protocol deviations which may affect the study outcome significantly will be used. The patients will be analysed according to the treatment group to which they were randomised, regardless of the actually treatment taken.

12.1.2 Safety analysis set

All randomised patients who received at least one dose of study medication will be included in the safety population. Throughout the safety results sections, erroneously treated subjects (eg,

those randomised to treatment A but actually given treatment B) will be accounted for in the actual treatment group.

12.2 Methods of statistical analyses

12.2.1 Analysis of efficacy data

All efficacy data will be listed by individual patient and summarised descriptively by treatment group.

Unless otherwise specified, for all changes (or percent changes) from baseline to a specific time point post-baseline as well as for glycemic therapeutic response definitions, analyses will be based on measurements available at that time point or the last post baseline measurement prior to the time-point, if no measurement is available at that time point, i.e., last observation carried forward (LOCF).

12.2.1.1 Primary analysis

For the primary efficacy analysis, the change from baseline in HbA1c at Week 12 will be analysed based on an analysis of covariance (ANCOVA) model including treatment group as a fixed effects and baseline as a covariate. Based on the ANCOVA model, the point estimates and 2-sided 95% confidence intervals for the mean changes within each treatment group as well as for the differences in mean changes between each of dapagliflozin treatment group and the placebo treatment group will be calculated. Pair-wise comparisons of dapagliflozin treatment groups vs. placebo group will be made with multiplicity of tests adjusted by Dunnett's method at overall 2-sided significance level 0.05.

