Clinical Study Protocol

Drug Substance Dapagliflozin
 Study Code D1692C00005
 Edition Number 1
 Date

A multicenter, randomized, double-blind, placebo-controlled, parallel group, Phase 2 trial to evaluate the efficacy and safety of dapagliflozin as monotherapy in Japanese subjects with type 2 diabetes mellitus who have inadequate glycemic control

Sponsor:

AstraZeneca K.K., [name]
 Bristol-Myers K.K., [name]

The following Amendment(s) and Administrative Changes have been made to this protocol since the date of preparation:

Amendment No.	Date of Amendment	Local Amendment No:	Date of Local Amendment
_____	_____	_____	_____
_____	_____	_____	_____
_____	_____	_____	_____
Administrative Change No.	Date of Administrative Change	Local Administrative Change No.	Date of Local Administrative Change
_____	_____	_____	_____
_____	_____	_____	_____
_____	_____	_____	_____

This submission /document contains trade secrets and confidential commercial information, disclosure of which is prohibited without providing advance notice to AstraZeneca, Bristol-Myers Squibb and opportunity to object.

PROTOCOL SYNOPSIS

A multicenter, randomized, double-blind, placebo-controlled, parallel group, Phase 2 trial to evaluate the efficacy and safety of dapagliflozin as monotherapy in Japanese subjects with type 2 diabetes mellitus who have inadequate glycemic control

Principal Investigator

The name of the investigators are described in Supplement A, “Investigations and Study Administrative Structure”.

Study centre(s) and number of subjects planned

Study Centres: Approximately 40 centres are planned for participation

Number of Subjects: 275 randomised Japanese subjects (55 subjects per treatment group)

Study period		Phase of development
Estimated date of first subject enrolled	August 2009	Phase 2
Estimated date of last subject completed	June 2010	

Objectives and Outcome variable(s)

Primary Objectives

Primary Objectives	Primary Outcome variable(s)
To compare the mean changes from baseline in glycosylated hemoglobin (HbA1c) achieved with each dose of dapagliflozin vs placebo after 12 weeks of double-blind therapy.	The primary efficacy endpoint is the change in HbA1c from baseline to Week 12 or the last post-baseline measurement prior to Week 12, if no Week 12 assessment is available. The term "change" here and hereafter refers to absolute change.

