3.1 Overall study design and flow chart

[figure not shown]
This is a Phase 2b, multicentre, randomized, 5-arm, parallel-group, double-blind, placebo-controlled study to evaluate the efficacy and safety of dapagliflozin in Japanese T2DM subjects with inadequate glycemic control on diet and exercise alone.

This study consists of an enrolment visit, a 6-week wash-out phase (Period A), a 4-week single-blind, placebo lead-in phase (Period B), a 12-week double-blind, placebo-controlled treatment phase (Period C), and a 4-week follow-up phase (Period D).

Subjects who have inadequate glycemic control ($\text{HbA1c} \geq 7\%$ but $\leq 10\%$) on diet and exercise alone at Visit 5 (1 week before randomization) are eligible to be randomised.

The study design is shown in [Figure 1](#).

Figure 1 Study flow chart

Enrolment visit (Visit 1)

Subjects will provide informed consent if not done before Visit 1, be enrolled and screened for all applicable inclusion and exclusion criteria, and submit laboratory samples.

There will be 4 types of subjects enrolled:

- Strictly treatment naïve subjects at enrolment, defined as never received medical treatment for diabetes (insulin and/or oral anti-hyperglycaemic agents)
- Relatively treatment naïve subjects at enrolment, defined as received medical treatment for diabetes for less than 30 days since diagnosis. In addition, during the 30-day period prior to enrolment did not receive oral anti-hyperglycemic medication for more than 3 consecutive or more than 7 non-consecutive days. Subjects also should not have a history of insulin therapy within 2 weeks of enrolment (with the exception of insulin therapy during a hospitalization for other causes or use in gestational diabetes).
- Subjects treated with anti-diabetic medication prior to enrolment, defined as previously treated with anti-diabetic medication but have not been treated within 6 weeks of enrolment
- Subjects treated with anti-diabetic medication up to enrolment. Only a single oral anti-hyperglycaemic agent or two agents with less than half of the approved maximal dose for each agent are allowed

Wash-out period - Period A (6 weeks; Visit 2 and Visit 3)

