In Period B, Single-blind placebo will be used to assess subject's compliance with treatment. Subjects must demonstrate good compliance with investigational products ($\geq 80\%$ and $\leq 120\%$) during Period B, and have HbA1c $\geq 7\%$ but $\leq 10\%$ at Visit 5 (1 week before randomisation) to be eligible for entry into Period C. Subjects will be withdrawn from the study if they do not meet these criteria, and must return all unused investigational products. The Investigators will assess adverse event and provide medical therapy that is clinically needed for the subject.

Double-blind, Placebo-controlled, Treatment Phase - Period C (12 weeks; Visit 6-13)

Eligible subjects will participate in a randomized, double-blind, placebo-controlled treatment phase (Period C). Subjects will be randomized to one of five treatment arms that include dapagliflozin 1 mg, 2.5 mg, 5 mg, 10 mg or placebo in a 1:1:1:1:1 ratio. Subjects will be followed for a total of 12 weeks on double-blind study medication, returning for a visit one week after start of treatment, and then approximately every 2 weeks for evaluation of safety and efficacy. Once a patient is randomised, all visits should be scheduled relative to Visit 6. Any slippage in time from one visit must not accumulate to affect other visits. Period C must be at least 81 days and at the most 87 days (12 weeks \pm 3 days). Subject should not take investigational products prior to study visit at Visit 7, 10 and 12 (Week 1, 6 and 10). Investigational products should be taken soon after completing the study visit examinations.

All randomised Subjects who do not complete Period C will complete Visit 13 (Week 12) study procedures as soon as possible but at the latest within 7 days after discontinuation of investigational products.

Visit 6 (Week 0):

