3.2 Rationale for study design, doses and control groups

This study is a randomized, double-blind, placebo-controlled study to assess the efficacy and safety of dapagliflozin in Japanese subjects with T2DM who have inadequate glycemic control. This study is also designed to be as similar as possible to the global phase 2b study (MB102008) in order to enable comparison of the efficacy and safety results between the two studies.

Placebo lead-in period is set to remove any bias regarding placebo effect. Patients receiving prior therapy will complete a 6-week washout period, and 4 weeks of placebo lead-in for a total washout period of 10 weeks to eliminate effects of the prior therapy. The reason for 10 weeks of washout is as follows:

- (a) Adequate washout of all prior oral anti-diabetic agents and their pharmacodynamic effects including the ones that have prolonged effects such as Pioglitazone
- (b) Stabilization of HbA1c after discontinuation of any oral anti-diabetic agents takes 8-12 weeks. 10 weeks of washout allows for an adequate stabilization of HbA1c after washout of oral anti-diabetic agents prior to randomization of patients to dapagliflozin versus placebo treatment arms in this study.

The Follow-up period is set to examine the reversibility of potential adverse events after taking the last dose.

Doses of dapagliflozin and control groups

Placebo-controlled study is essential to evaluate the blood glucose-lowering effects of dapagliflozin.

In this study, dapagliflozin doses 1 mg, 2.5 mg, 5 mg and 10 mg were chosen based on efficacy, pharmacodynamic and safety data from the global phase 1 and 2 studies, and the Japan phase 1 studies. This dose range is supported by the following reasons:

- In the global phase 1 and 2a studies, maximal glucosuria was seen at the 10 to 20 mg dose level. Doses ≥ 20 mg only increased the duration of glucosuria. In the global phase 2b study (MB102008), glucosuria appeared related to dose, with maximal glucosuria seen at the 20 and 50 mg doses.
- In the global phase 2b study (MB102008), dapagliflozin improved glycaemic parameters throughout the dose range of 2.5 mg to 50 mg daily, with most of the efficacy realized within the dose range of 2.5 mg to 10 mg. There was no apparent dose relationship beyond 10 mg for HbA1c, though there was evidence for a continued dose-response relationship up to 50 mg with respect to FPG change.

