5.2.1 Procedures for randomisation

Randomisation codes will be assigned at Week 0 of Period C.

The investigational product will be allocated by EPS Co., Ltd.. Key codes (drug number and the information of the allocated drugs) will be prepared by EPS Co., Ltd. and would be delivered together with the investigational product to the study sites.

Randomization to study treatment will be done in balanced blocks for each centre in order to ensure approximate balance among the 4 arms of dapagliflozin groups and the placebo group. Subjects will be randomized strictly sequentially, as subjects are eligible for randomization. If

a subject discontinues from the study, the subject number will not be reused, and the subject will not be allowed to re-enter the study.

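### The primary ANCOVA leaves out centre, the blocking factor, and recorded washout status; the analysis is valid, but a small, cheap gain in precision is available

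*Protocol*

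**What the plan says.** The synopsis and Section 12.2.1.1 give the same primary model for change in HbA1c at Week 12: an "analysis of covariance (ANCOVA) model including treatment group as a fixed effects and baseline as a covariate". Dunnett's method is applied to the four dose-placebo comparisons. Sections 12.2.1.2 and 12.2.1.3 use a similar model for FPG and for the tertiary ANCOVAs.

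Section 5.2.1 makes centre a design factor: "Randomization to study treatment will be done in balanced blocks for each centre in order to ensure approximate balance". The synopsis adds "Approximately 40 centres are planned for participation", for 275 subjects in five arms allocated "in a 1:1:1:1:1 ratio" (Section 3.1). The protocol gives no reason for leaving centre out of the model.

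On prior therapy, Section 3.1 says "There will be 4 types of subjects enrolled". Only those on medication up to enrolment go through the washout, Period A; the other three types skip it. Section 3.2 says "Stabilization of HbA1c after discontinuation of any oral anti-diabetic agents takes 8-12 weeks", then judges the total of 10 weeks off drug before randomisation to be adequate. Prior-treatment type is not a randomisation factor.

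**The concern.** Two separate matters are involved.

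- **Centre.** Blocking within centre takes between-centre variation out of the treatment contrast. A model without centre still counts that variation as residual error, so if centres differ in HbA1c change, the reported standard error is larger than the true sampling error.
- **Washout status.** Subjects reach Week 0 by different routes. Three types must have HbA1c of 7-10% off drug at Visit 1 and again at Visit 5. The fourth must be at 8% or below, on drug, at Visit 1, and at 7-10% at Visit 5 after stopping. The same baseline value could therefore precede a different later course. Ten weeks lies inside the protocol's own 8-12 week stabilisation range, so some residual movement at baseline is possible.

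At stake is the width of the confidence intervals and a little power, for the primary endpoint and for every endpoint analysed with the same model. Bias is not in question.

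**Working it through.** **The plan's own figure.** From Section 12.3: difference 0.54, SD 0.74, 53 analysed per arm, four Dunnett comparisons at two-sided 0.05.
- Dunnett critical value (4 comparisons, correlation 0.5, 260 df): 2.457.
- SE of a difference: 0.74 × √(2/53) = 0.144.
- Noncentral t power: 90.2% at 53 per arm. The stated 90% reproduces with no covariate at all.

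**Washout status.** The protocol gives neither the share washed out (p) nor the extra drift (d). Assumed: p = 0.3-0.5, d = 0.2-0.4 percentage points, with 0.74 as the SD after baseline adjustment.
- Variance share = p(1−p)d²/0.74².
  - Low end: 0.3 × 0.7 × 0.04/0.5476 = 1.5%.
  - High end: 0.5 × 0.5 × 0.16/0.5476 = 7.3%.
- SE reduction = 1 − √(1 − share) = 0.8% to 3.7%.
- For reference, a 5% share gives 91.8% power at 53 per arm.

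**Chance imbalance.** The SD of the shift in one dose-placebo difference is d√(2p(1−p)/53), which runs from 0.018 to 0.039. Squared and divided by 0.144², this gives 1.5% to 7.3%, the same shares as above. It is the same quantity seen from another side, and the planned interval already covers it.

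**Centre.** 275/40 = 6.9 subjects per centre, or 1.4 per arm. The protocol gives no ICC; assumed 0.02-0.05. The upper bound on the SE reduction is 1 − √(1 − ICC) = 1.0% to 2.5%, ignoring degrees of freedom and incomplete blocks.

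**Simulation** (265 analysed, 40 centres, blocks of 5 or 10, both assumed because block size is not stated; 40% washed out in the settings with drift):

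| Setting | Result |
|---|---|
| Two-term model, ICC 0.10-0.20 | model SE about 0.144; actual SD of the estimate mostly 0.133-0.139 |
| Centre as fixed effect, ICC 0-0.02 | power falls by up to about 2 points |
| Centre as fixed effect, break-even | ICC about 0.03-0.07 |
| Centre random plus Period A yes/no, both effects zero | power 0.898 against 0.901 for the two-term model |
| Centre random plus Period A yes/no, ICC 0.02-0.10, drift 0.3 | gain of about 1-3 points |

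The first row shows that ignoring centre errs on the conservative side. The fixed-effect rows show why 40 fixed centre effects (39 df) are the wrong remedy. The last two rows show that the random-effect form costs essentially nothing when it is not needed.

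**The case against.** The strongest case against the point is that nothing in the plan is wrong. The sample size rests on an unadjusted two-sample t-test and reaches 90% without help from either factor. HbA1c comes from one central laboratory and is analysed as change from each subject's own Week 0 value with baseline as covariate, so much of any difference in level between centres is already removed. Prior-treatment type was never a randomisation factor, so leaving it out contradicts nothing in the design. The SAP promised in Section 12 is not at hand and may add adjusted analyses. All of this stands. It limits the size of the point, but it does not explain why the stated primary model omits the factor on which randomisation is blocked.

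Three stronger readings are tempting, and the documents do not support them.

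- A reader might infer that prior treatment drives HbA1c drift after baseline. The protocol does not say so. Section 3.2 judges 10 weeks adequate, and Section 3.1 has washout starting at Week -10 at the latest, so it may last longer. Residual drift is only an inference from 10 lying between 8 and 12.
- A reader might infer that the plan throws away precision on which its power depends. It does not, because the power calculation uses no covariate.
- A reader might count chance imbalance in washed-out subjects as a second harm. As shown above, it is part of the same variance share.

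The objection that adjusting for centre can lose power is correct for fixed centre effects only.

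**Conclusion.** The omission is real, and its effect is small. The two-term ANCOVA is valid, and if centres differ it is mildly conservative. Adding both terms would give roughly 1-3 points of power under the assumed ranges (30-50% washed out, drift difference 0.2-0.4 points, centre ICC 0.02-0.05, with 0.10 also simulated), and close to zero if neither factor matters. None of these inputs is in the protocol, so the omission is certain but the size of the gain is not. Nothing here puts the trial's conclusions at risk. This is a cheap improvement of low severity.

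**What to change.** Before unblinding, by amendment or in the SAP:
- Add washed-out status (Period A yes/no) as a fixed effect and centre as a random effect to the primary ANCOVA, alongside treatment and baseline HbA1c.
- Apply Dunnett's method to the adjusted dose-placebo differences.
- Use the same model for FPG and the tertiary ANCOVAs, with each endpoint's own baseline.
- Keep the two-term ANCOVA as a sensitivity analysis.
- Do not fit 40 fixed centre effects.

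If the sponsor prefers to keep the two-term model as primary, it should say why the blocking factor is left out and pre-specify the adjusted model as a sensitivity analysis.

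The cost is wording, a slightly more complex model and 1 df for the Period A term. No new data or subjects are needed, since both factors are known by randomisation.

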12.3 Determination of sample size

The sample size for this study is calculated based upon the results observed in a similarly designed study for dapagliflozin (MB102008). From that study, the mean value and SD for the HbA1c change from baseline was -0.54% and 0.74%, respectively, as estimated from the the placebo-corrected change in the 5 mg group. The sample size calculation based on these results is considered appropriate, even though a smaller reduction in HbA1c could also be considered clinically meaningful. Then with 53 subjects per treatment group in the full analysis set, there is 90% power to detect a difference in mean change from baseline of 0.54% for HbA1c between any given dapagliflozin group and placebo using a 2-sample t-test at the overall 2-sided significance of 0.05, adjusted for multiplicity (4 tests against placebo) by Dunnett's method. Assuming a similar proportion (4%) of randomised patients are excluded from the full analysis set as seen in Study MB102008, 55 subjects per treatment group are needed to be randomised.

The sample size for this study was selected to be consistent with the research hypothesis as described in Section 1.2.

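### Dunnett's method, read as single-step, is valid and meets the planned 90% power per dose, but step-down Dunnett would control the same error rate with more power on the primary endpoint at almost no cost

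*Protocol*

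**What the plan says.** Section 12.2.1.1 analyses the Week 12 change in HbA1c by ANCOVA with treatment and baseline. It then states: "Pair-wise comparisons of dapagliflozin treatment groups vs. placebo group will be made with multiplicity of tests adjusted by" Dunnett's method, at an overall two-sided level of 0.05. It also asks for two-sided 95% confidence intervals for each dose-placebo difference, without saying whether these are simultaneous or unadjusted.

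Section 12.3 sizes the trial with the same adjustment: "at the overall 2-sided significance of 0.05, adjusted for multiplicity (4 tests against placebo"). Its inputs are "the mean value and SD for the HbA1c change from baseline was -0.54% and 0.74%, respectively, as estimated from" the placebo-corrected change in the 5 mg group of the earlier global Phase 2b study. The result is given per dose: "there is 90% power to detect a difference in mean change from baseline of 0.54% for HbA1c between any given dapagliflozin group and placebo", with 53 per group in the full analysis set.

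Three other places bear on the point. The primary objective (section 2.1) compares each dose with placebo, and no section sets a success rule or power target for all four doses jointly. Section 3.2 says that the 1 mg arm is there to confirm a sub-therapeutic dose. Section 12.3 concedes that a reduction smaller than the one used for sizing could also matter clinically.

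**The concern.** In single-step Dunnett every dose must pass the critical value for four comparisons, even when the other three have already been declared significant. The step-down form relaxes the critical value after each rejection. It is a closed test built on the same statistics and keeps strong control of the family-wise error at 0.05. It rejects everything that single-step rejects, and sometimes more.

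The main reason to stay with single-step is that simultaneous confidence intervals follow from it directly. Section 12.2.1.1 does not ask for such intervals. What is at stake is power on the primary endpoint. The loss is largest for a dose with a weaker effect tested beside stronger ones, which is the comparison that informs where the effective range starts.

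**Working it through.** **Inputs.** From section 12.3: n = 53 per group, difference 0.54, SD 0.74, family-wise two-sided 0.05, four tests. From section 3.1: "dapagliflozin 1 mg, 2.5 mg, 5 mg, 10 mg or placebo in a 1:1:1:1:1 ratio", so any two dose-placebo statistics have correlation 0.5. Error df = 5 × (53 − 1) = 260 (the baseline covariate takes one more, with no visible effect on the results).

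**Critical values for |t|**, by numerical integration:

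| Comparisons still in play | Single-step | Step-down |
|---|---|---|
| 4 (largest statistic) | 2.457 | 2.457 |
| 3 | 2.457 | 2.363 |
| 2 | 2.457 | 2.224 |
| 1 (smallest statistic) | 2.457 | 1.969 |

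The value 2.457 corresponds to a per-test two-sided level of 0.0147.

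**Reproducing the plan's figure.** Standard error of a difference = 0.74 × √(2/53) = 0.1438. Noncentrality = 0.54 / 0.1438 = 3.76. Power = P(|T| > 2.457) for a noncentral t with 260 df = 90.2%. The stated 90% therefore reproduces with the single-step critical value applied to every dose.

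**Comparison of the two methods**, by simulation of 1,000,000 trials per scenario with 53 per group and SD 0.74. Only the 0.54 at 5 mg comes from the protocol; every other dose effect is an assumption.

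| Assumed true effects (1 / 2.5 / 5 / 10 mg) | Quantity | Single-step | Step-down |
|---|---|---|---|
| 0.54 at all four | power per dose | 90.2% | 94.7% |
| 0.54 at all four | all four significant | 74.7% | 88.2% |
| 0.54 at all four | at least one significant | 99.1% | 99.1% |
| 0.35 / 0.54 / 0.54 / 0.54 | power for 1 mg | 49% | 66% |
| 0.27 / 0.54 / 0.54 / 0.54 | power for 1 mg | 28% | 46% |
| 0 / 0.54 / 0.54 / 0.54 | 2.5, 5 and 10 mg all significant | 79% | 85% |

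**Family-wise error** (probability of any false rejection):

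| True state | Single-step | Step-down |
|---|---|---|
| No dose works | 5.0% | 5.0% |
| One dose inert, three at 0.54 | 1.5% | 4.2% |
| Three doses inert, one at 0.54 | 3.9% | 4.8% |

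Step-down stays within the 5% level in each case, up to simulation error.

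**The case against.** The strongest reply is that nothing here is an error. Single-step Dunnett controls the family-wise error in the strong sense. The only power that the protocol promises is 90% for any given dose at a difference of 0.54, and the method delivers it. That stands.

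A reader might infer from the 75% figure that the trial has only a three-in-four chance of success. The documents do not support this. No section makes significance at all four doses a criterion. Section 3.2 expects 1 mg to be sub-therapeutic, so significance there is not the plan's aim. Both the 75% and the 88% also require the full 0.54 effect at every dose, although section 12.3 takes that figure from the 5 mg group alone. The chance that at least one dose is significant is 99.1% with either method.

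A reader might also infer that the protocol expressly fixes the single-step form. It says only Dunnett's method. Single-step is the usual reading and fits the sample size, but the sizing does not exclude step-down, under which 90% would be a lower bound. Section 12 refers to an SAP, which is not at hand and may name the variant.

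Step-down also has real costs. If 1 mg is inert while the other doses work, it is usually tested at 1.969, and its false-positive risk rises from about 1.5% to 4.2%. Given the stated purpose of that arm, a sponsor could reasonably prefer the stricter bar. Simple matching simultaneous intervals are lost as well. Neither cost defeats the suggestion: 4.2% is within the level that the plan itself sets, and section 12.2.1.1 does not ask for simultaneous intervals. The opposite mistake matters too. If 1 mg truly lowered HbA1c by 0.35%, single-step would miss it in about 51% of trials and step-down in about 34%.

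**Conclusion.** The point holds as an efficiency gain, not as a fault in validity or a missed target. Under the plan's own n and SD, and with equal effects of 0.54 at every dose, step-down adds about 4.5 percentage points of power per dose (90.2% to 94.7%). With 1 mg inert, it adds about 7 points to the chance that the other three doses are all significant (78.6% to 85.3%). The largest gain is for a weaker dose beside stronger ones: about 17 points for 1 mg at an assumed effect of 0.35.

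The conclusion rests on reading section 12.2.1.1 as single-step, on a common SD of 0.74 and on 53 analysed per group. It also rests on dose effects that, apart from 0.54 at 5 mg, are assumed. Error control at 5% does not depend on the assumed effects.

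**What to change.** State in section 12.2.1.1, and in the SAP before unblinding, that step-down Dunnett is applied to the four two-sided ANCOVA t statistics ordered by absolute size. The largest is compared with the four-comparison critical value, the next with the three-comparison value, then the two-comparison value, then the unadjusted value. Testing stops at the first non-rejection, and step-down adjusted p-values are reported. Label the 95% confidence intervals for the dose-placebo differences as unadjusted.

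Keep the sample size, and describe the 90% in section 12.3 as a lower bound on power per dose. If the sponsor prefers the stricter bar for 1 mg or wants simultaneous intervals, the protocol should say that single-step is intended and give that reason.

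The cost is a sentence or two of text. No patient, visit, model or data collection changes.
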